8.3.2.2 Secondary outcomes

- Incidence of AEs.
- Incidence of SAEs (see Sections 10.1 and 10.2).

8.3.2.3 Further outcome

• To assess acceptability and tolerability of paediatric formulation.

Acceptability is defined as the overall ability and willingness of the patient and/or parent (legal guardian) to use the medicinal product as intended.

Tolerability is measured as premature treatment discontinuation, treatment interruption, and adherence to trial medication.

Assessment of acceptability and tolerability.

The overall clinical assessment of acceptability and tolerability will be performed by the parent / legal guardian and investigators by completing a standardized questionnaire. In between baseline and study final visits, the parent /legal guardian will be asked to document any failed or missed intake of medication (e.g., the patient did not swallow the medication, or doses missed, etc.) and provide this documentation to the investigator. The parent / legal guardian will be instructed to inform the

1160.307 PASS NIS Protocol

Proprietary confidential information © 2024 Boehringer Ingelheim International GmbH or one or more of its affiliated companies

investigator immediately if two or more consecutive doses of study medication are missed or not taken correctly.

Assessment of the representativeness of the study cohort.

Screening Log with details of all patients requiring anticoagulation due to acute VTE treatment and/or secondary VTE prevention will be used for assessment of the representativeness of the study cohort, when all required anticoagulation patients will be compared with patients enrolled in the PASS.

All parents/legal guardians will be asked to sign informed consent before the screening procedures. Screening Log will contain demography, details of conditions that require anticoagulation, conclusion on entry in the PASS or comments on reasons for screening failure.

The safety outcomes will be evaluated based on the on-treatment period, i.e., from start of DE administration (index date) up to DE administration discontinuation + 3 days of REP or switch to other anticoagulation therapy + 3 days of REP or planned end of observation time, whatever occurs earlier.

8.3.3. Covariates

Detailed information on paediatric patients under 2 years of age and DE administration will be collected as follows:

At Screening/Baseline:

- Demographics (e.g., age, weight, gender, race, country),
- Hospitalisation details, type of paediatric department (e.g., neonatology, cardio-surgery, ICU, haematology, etc.) and procedures related to VTE diagnostic modalities,
- Medical history including concomitant medications history (administered within 14 days prior to informed consent),
- Baseline conditions,
- Acute VTE characteristics as type of VTE, symptomatic / asymptomatic, location; VTE characteristics obtained according to standard diagnostic modalities and local protocols,
- Available characteristics of the most recent VTE event (as specified above) for prevention of recurrent VTE group,
- Presence of post-thrombotic syndrome (PTS); if PTS present, used diagnostic scale and score should be indicated,
- VTE clinical risk factor(s),
- Initial DE dosage and formulation.

At Follow up:

- Concomitant treatment and procedures,
- Any changes in DE dosage(s) and formulations with corresponding age and weight
- Duration of DE administration,

The safety outcomes will be evaluated based on the study observational period defined above (Section 8.1 "Study design" and Section 8.3.2 "Outcomes").

8.4 DATA SOURCES

Newly collected data and/or data collected from medical records will be entered by the site directly in an electronic data capture (EDC) system via an Internet portal.

All data will be obtained by qualified clinicians by an appropriate objective method used in standard practice.

All sites will be fully trained for using the EDC system and the BI AE/SAE reporting procedure. It is the Principal Investigator's responsibility at each study site to ensure the accuracy of the data provided to the program by any site staff that is trained for the program data collection.

8.5 STUDY SIZE

1160.307 PASS NIS Protocol

The study sample size is based on the anticipated usage of dabigatran for acute VTE treatment and prevention of recurrent VTE.

The target sample size of 50 evaluable patients is planned to be enrolled from approximately 30 paediatric sites over a 2-year period. Patients who completed acute VTE treatment and continued DE anticoagulation due to unresolved VTE risk factors will be considered as one unique patient Approximately 10 EU/EEA countries are planned to engage in this study.

The feasibility to reach this target sample size is based on the previous experience in the DE paediatric VTE clinical trial program (see Section 8.2) and data from existing registries [R11-4525].

In the DIVERSITY study with acute VTE study population from 99 globally initiated sites, 65 were active. However, only 15 of these sites enrolled 35 children under 2 years of age with acute VTE within an approximate one-year enrolment period. In the long-term secondary VTE prevention study, from 62 active sites, 6 sites enrolled 9 patients under 2 years of age within approximately one year. Most of the young patients were enrolled from the sites outside EEA. However, in contrast to the current PASS, selection of the sites in these studies was not initially focused on their ability to enrol children under 2 years of age.

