However, limited evidence is available in early age children (from birth to < 2 years) for treatment of VTE and prevention of recurrent VTE. This age group also demonstrate the most marked differences from adults in hemostaseology [R15-4967]. The results of acute VTE treatment in this age group were evaluated in 35 cases of the DIVERSITY study, where 22

1160.307 PASS NIS Protocol c3592 Proprietary confidential information © 2024 Boehringer Ingelheim International GmbH or one or more of its affiliated companies

patients received DE and 13 received SOC [P20-07911]. The long-term secondary VTE prevention study evaluated 9 children in this early age group [c29754273-01]. The limited number of neonates and infants evaluated in the DE paediatric program was connected with multiple challenges, including the relatively rare condition, a critically ill population with life-threatening comorbidities, use of aggressive treatments, limited blood volumes that can be drawn for study purposes and, finally, parental consent that is often difficult to obtain in young children with acute serious conditions [R11-4524, P17-11774, P19-00949, R20-3318]. Thus, post-authorization data collection is planned to characterize the safety profile of dabigatran in children under 2 years of age. The aim of this PASS is to evaluate the safety of all paediatric patients under 2 years of age receiving DE in a routine clinical practice setting.

7. **RESEARCH QUESTION AND OBJECTIVES**

The objective of this study is to evaluate the safety of DE for VTE treatment and prevention of VTE recurrency in children from birth to < 2 years of age in a routine clinical practice setting.

Primary objective:

• To estimate the incidence of any bleeding event defined as Major Bleeding Event (MBE) or Non- Major Bleeding Event (Non-MBE) among the children under 2 years of age on DE administration.

Secondary objective:

- To estimate the incidence of AEs.
- To estimate the incidence of SAEs.

Further objective:

• To assess acceptability and tolerability of paediatric formulation.

8. **RESEARCH METHODS**

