8.2 SETTING

8.2.1 Study sites

The PASS is intended to be available to paediatric hospitals and paediatric departments of European Economic Area member states, where VTE paediatric patients under 2 years of age are treated, depending on country regulations and requirements. Approximately 30 paediatric study sites with experience in VTE anticoagulation treatment and prevention will be selected and initiated by Q4 2022. Every effort will be made to identify sites where paediatric use of DE is available.

The selection of study sites for the 1160.307 study will be focused on specialised paediatric units treating neonates, infants, and young children.

1160.307 PASS NIS Protocol

Proprietary confidential information © 2024 Boehringer Ingelheim International GmbH or one or more of its affiliated companies

Previous experience from the DIVERSITY and prevention of secondary VTE studies support the assumption that approximately 30 specialised paediatric sites focusing on treatment of neonates and infants with VTE risk factors will be able to enrol and collect safety data from overall 50 evaluable children administered DE for VTE treatment and prevention. In addition, experience from the previous dabigatran VTE paediatric program indicates on a potential varying enrolment rate in the selected sites and variations in the clinical management mainly in terms of duration of anticoagulation based on investigator's judgment. However, these variations related to the baseline clinical conditions underline acute VTE event or VTE risk factors that affect safety outcomes, e.g., bleeding events rate in patients with thrombophilia is usually lower than in unselected VTE population under anticoagulation [R21-0986]. The collected safety data from a variety of paediatric units with early age children will reflect routine medical care in EU/EEA when receiving DE anticoagulation.

Based on the previous BI VTE program experience, neonates and infants with acute VTE requiring DE administration are localised in the following paediatric units:

- neonatology departments, where target conditions are umbilical thrombosis, cerebral vein thrombosis, central line related-VTE, etc.
- paediatric surgery, paediatric cardiology, paediatric cardio- surgery, intensive care units, and paediatric haematology departments where target conditions are central line / implantable devices related-VTE, cyanotic congenital heart disease, venous malformations, leukaemias etc.

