Patients who require anticoagulation for secondary VTE prevention are evaluated mostly in paediatric haematology, paediatric cardiology, and paediatric cardio-surgery departments.

During the approximate 1.5-year enrolment period every effort will be made to support investigators to include the paediatric patients requiring dabigatran anticoagulation in this study. These efforts will include communications with investigators using digital resources and face to face communications, presentation of the results and enrolment strategies of the previous published studies on DE, focused on early age children [P20-07911].

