8.2.2 Study population

Paediatric patients from birth to < 2 years of age considered by investigator after screening as eligible for DE treatment of acute VTE or secondary prevention of recurrent VTE will be enrolled in the PASS and evaluated for up to 3 months in case of acute VTE treatment, and up to 6 months in case of prevention of recurrent VTE.

Patients after completion of acute VTE treatment may continue anticoagulation as secondary VTE prevention due to unresolved VTE risk factors in accordance with investigator's judgment. Total observational period for this group, which include VTE treatment and prevention will be also up to 6 months duration. Further anticoagulation, if required due to unresolved VTE risk factors, will be continued outside the study setting.

Inclusion criteria:

- Written informed consent from parents/care givers,
- Children from birth to less than 2 years of age,
- Initiation of DE administration:
 - for treatment of VTE or/and
 - prevention of recurrent VTE due to presence of unresolved clinical VTE risk factor(s).

Exclusion criteria:

1160.307 PASS NIS Protocol

- Participation in any Randomised Clinical Trial or use of any investigational product,
- Any contraindications to DE according to the EU SmPC.

Paediatric population will be stratified into two groups according to the EU DE SmPC:

- children anticoagulated with dabigatran due to acute VTE treatment
- children anticoagulated with dabigatran for prevention of recurrent VTE due to the presence of an unresolved VTE clinical risk factor.

Patients who completed acute VTE treatment and continued DE anticoagulation due to unresolved VTE risk factors will be considered as one unique patient. However, safety outcomes of each anticoagulation period will be evaluated within the corresponding cohort.

The target sample size for the study is considered to be 50 evaluable patients enrolled from approx. 30 paediatric sites over an approximate 1.5-year period with a total approximate 2-year study duration.

The enrolment period is planned from Q4 2022 (FPI) to the Q2 2024 (LPI) depending on the availability of DE paediatric formulation (granules) on the market.

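### Section 8.5 gives 2 years of enrolment where section 8.2 gives about 1.5, and at the earlier trials' active-site rates 30 sites would yield about 31 children in 1.5 years (41 in 2), not 50

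*Protocol*

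**What the plan says.** Section 8.5 (Study size): "The target sample size of 50 evaluable patients is planned to be enrolled from approximately 30 paediatric sites over a 2-year period". Section 8.2.2 (Study population) instead has "50 evaluable patients enrolled from approx. 30 paediatric sites over an approximate 1.5-year period with a total approximate 2-year study duration" and dates enrolment from Q4 2022 to Q2 2024. Section 8.2.1 (Study sites) agrees with 8.2.2: "During the approximate 1.5-year enrolment period every effort will be made" to support recruitment. Section 5 (Milestones) runs data collection from Q4 2022 to Q3 2024.

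On feasibility, section 8.2.1 says that experience from DIVERSITY and the secondary prevention study supports the assumption that about 30 specialised sites "will be able to enrol and collect safety data from overall 50 evaluable children administered DE for VTE treatment and prevention". Section 8.5 bases feasibility on the same programme and on registry data for which it gives no figures.

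The experience itself is reported in section 8.5. In DIVERSITY, 99 sites were initiated and 65 were active, and "only 15 of these sites enrolled 35 children under 2 years of age with acute VTE within an approximate one-year enrolment period". In the secondary prevention study, "from 62 active sites, 6 sites enrolled 9 patients under 2 years of age within approximately one year". Section 6 adds that, of the 35 DIVERSITY children, 22 "patients received DE and 13 received SOC". Section 8.5 also says that most of these young patients came from outside the EEA, and that the earlier sites, unlike those of this study, were not chosen for their ability to enrol this age group.

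**The concern.** There are two separate problems in how the study size is justified.

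First, the enrolment period in section 8.5 conflicts with sections 8.2.1 and 8.2.2. It looks as if the total study duration was carried over as the enrolment duration. The slip makes the target look easier, because it spreads 50 children over more site-years.

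Second, the protocol presents earlier experience as support for 50 children from 30 sites and then reports counts that give fewer when scaled to 30 sites. The difference has to come from a gain in recruitment per site, which is described but not quantified.

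The study tests no hypothesis, so the number enrolled is what decides how wide the confidence intervals will be. Section 8.2.4 also makes failure to meet enrolment goals a ground for discontinuation. A reader should therefore be able to see what the target assumes.

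**Working it through.** **Enrolment period.** Sections 8.2.1 and 8.2.2: about 1.5 years, Q4 2022 to Q2 2024. Section 8.5: 2 years. Under section 5, data collection runs from Q4 2022 to Q3 2024, which is 2 years at most. Under section 8.1, each child is observed for up to 3 months (acute treatment) or up to 6 months (prevention). Two years of enrolment would use the whole data-collection window and leave nothing for observing the last children.

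**The plan's own figure.** The protocol gives no formula behind 50; it bases the number on anticipated usage. The check is therefore whether the cited experience yields 50.

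**Inputs.** 30 sites. DIVERSITY: 35 children under 2 years (22 on DE) at 15 of 65 active sites in about one year. Secondary prevention study: 9 children at 6 of 62 active sites in about one year.

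**Rate per active site-year.**
- All children: 35/65 + 9/62 = 0.538 + 0.145 = 0.684
- DE-treated only: 22/65 + 9/62 = 0.338 + 0.145 = 0.484

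**Expected yield = sites × years × rate.**

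| | 1.5 years (45 site-years) | 2 years (60 site-years) |
|---|---|---|
| All children | 45 × 0.684 = 30.8 | 60 × 0.684 = 41.0 |
| DE-treated only | 45 × 0.484 = 21.8 | 60 × 0.484 = 29.0 |

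All four values are below 50. With the 99 initiated DIVERSITY sites as denominator, the 1.5-year figure for all children is 45 × (35/99 + 9/62) = 22.4.

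**Rate that the target needs.**
- 1.5 years: 50/45 = 1.11 per site-year, and 1.11/0.684 = 1.6 times the earlier active-site rate
- 2 years: 50/60 = 0.83 per site-year, and 0.83/0.684 = 1.2 times

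The 2-year wording thus lowers the required rate from 1.11 to 0.83.

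**The same gap as a share of enrolling sites, over 1.5 years.**
- At the DIVERSITY enrolling-site rate (35/15 = 2.33 per year): 50/(1.5 × 2.33) = 14.3 sites
- At the pooled enrolling-site rate ((35 + 9)/(15 + 6) = 44/21 = 2.10 per year): 50/(1.5 × 2.10) = 15.9 sites

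That is about 14 to 16 of 30, or roughly half. The earlier trials saw 15/65 = 23% and 6/62 = 10%.

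**What the size means for precision.** For zero events the Wilson 95% upper limit is z²/(n + z²) with z² = 3.84. At n = 50 it is 3.84/53.84 = 7.1%; at n = 31 it is 3.84/34.84 = 11.0%.

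**The case against.** The strongest reply is that the figure of 31 depends on the denominator. Active sites in trials of children up to 18 years are a poor model for sites picked because they treat neonates and infants. Per enrolling site, the same counts give much more over 45 site-years: 45 × 22/15 = 66 (acute, DE-treated only), 45 × 44/21 = 94 (pooled) or 45 × 35/15 = 105 (acute, all). Fifty lies between the two sets of figures. This stands, and it rules out reading 31 as a forecast or 50 as a ceiling. It does not restore the claim of support: the enrolling-site figures assume that all 30 sites enrol, they condition on having succeeded, and most of those children came from outside the EEA.

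Site selection is also not the only favourable factor mentioned. The protocol cites registry data, seeks sites where paediatric DE is available, plans recruitment support and requires no special study procedures. It openly reports the low earlier counts and lists market uptake as a limitation. All of this is fair, but none of it comes with a number.

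Counting only the 22 DE-treated children is pessimistic. The other 13 went to a comparator arm, and this study has none, so some of them might have received DE here. In the other direction, 31 is partly generous: it adds both indications' rates at every site and makes no deduction for the EEA restriction.

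Two stronger readings are tempting. A reader might put a Poisson probability on reaching 50 and call it negligible. That treats sites as alike, although 50 of 65 and 56 of 62 active sites enrolled no child under 2, so the probability would be falsely precise. A reader might also infer that the protocol promises the precision of 50 children. It makes no precision statement, and the reported intervals will use the number actually enrolled.

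**Conclusion.** The point holds in two parts.

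The enrolment period in section 8.5 is inconsistent with sections 8.2.1 and 8.2.2 and does not fit the data-collection dates. This rests on the text alone.

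The cited experience does not by itself yield 50. At earlier active-site rates the shortfall is 50 − 31 = 19 children over 1.5 years, or 50 − 41 = 9 over 2 years; the DE-only figures of 22 and 29 are a cautious lower bound. These yields assume that all 30 sites are open throughout, that each recruits for both indications at the sum of the two earlier rates, and that active sites are the right comparison. The target then implies a gain of about 1.6-fold over 1.5 years, which the protocol leaves unquantified.

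The documents do not show that 50 is out of reach. If about half the sites recruit like the earlier enrolling ones, it is reached. What is missing is a statement that the target depends on this.

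**What to change.** In section 8.5:

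- Replace the 2-year enrolment period with the approximately 1.5 years of section 8.2, keeping 2 years for total study duration only.
- State the expected yield at the earlier active-site rates (about 31 from 30 sites in 1.5 years) next to the target of 50, with the gain from site selection that the target assumes: about 1.6-fold, or about 14 to 16 of 30 sites recruiting like the earlier enrolling sites.
- Qualify the statement, here and in section 8.2.1, that earlier experience supports 50, so that it is conditional on that gain.
- Optionally, give the Wilson upper limit for zero events at 50 and at 31 children (7.1% and 11.0%).

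The cost is a text change. The expected size will read less favourably than it does now; no extra patients or sites are needed.

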8.6 DATA MANAGEMENT

Newly collected data and/or data collected from medical records will be entered by the site directly in an electronic data capture (EDC) system via an Internet portal. All participating sites will have access to the data entered regarding the individual site of its own enrolled subjects. All sites will be fully trained on using the online data capture system, including the electronic case report form completion guidelines. A data management plan will be created before data collection begins and will describe all functions, processes, and specifications for data collection and validation. Real time data cleaning will be performed through EDC. The eCRFs will include programmable edit checks to obtain immediate feedback if data are missing, out of range, illogical or potentially erroneous at the time of data entry. The selected vendor will coordinate the data collection and data management including the necessary quality measures, according to the vendor standard operating procedures (SOPs).

Full details of the data management plan are documented in a separate NIS-Data Management and Review Plan (NIS-DMRP).

1160.307 PASS NIS Protocol

Proprietary confidential information © 2024 Boehringer Ingelheim International GmbH or one or more of its affiliated companies

8.7 DATA ANALYSIS

The statistical analysis plan for the study is summarized below. Full details of the statistical analysis will be documented in the SEAP, which will be finalized before the end of data collection. Safety outcomes from this single-arm study will be interpreted in the context of findings from the paediatric clinical developmental program, i.e., acute VTE treatment (DIVERSITY) and secondary VTE prevention studies.

All computations and generation of tables, listings and data for figures will be performed using SAS® version 9.4 or higher (

8.7.1 Main analysis

As this is a descriptive non-interventional, single-arm study, no hypotheses will be tested, rather all variables will be presented in summary using descriptive statistics (absolute and relative frequencies, means, standard deviations, medians, ranges, minimum and maximum values, 95% confidence intervals [CI] and incidences as appropriate for the nature of the variables (i.e., categorical, or continuous))

Safety outcomes will be summarized as incidence with 95% CIs (using Wilson method). All AE/ verbatim terms will be recorded and coded using the Medical Dictionary for Regulatory Activities (MedDRA). Analysis of AEs and other outcomes will be based on treatment emergent events and on all patients, who were treated with dabigatran at least once. Treatment-emergent events are defined as events occurring from start of DE administration (index date) up to DE administration discontinuation + 3 days of Residual Effect Period (REP) or switch to other anticoagulation therapy or planned end of observation time, whatever occurs earlier.

Concomitant medications will be coded according to the World Health Organisation Drug Dictionary (WHO-DD).

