8.1 STUDY DESIGN

The DE Post-Authorization Safety Study (PASS) for VTE treatment and prevention of recurrent VTE in children under 2 years of age is designed as a prospective, non-interventional European multinational multi-centre, single-arm cohort study based on newly collected data of patients anticoagulated by DE for acute VTE treatment or prevention of recurrent VTE.

The study is designed to collect and evaluate DE safety in the context of routine anticoagulation care provided in the EU/EEA for children under 2 years of age. The duration of the study will be up to 2 years with the goal to enrol 50 evaluable patients under DE administration. Approximately 10 EU/EEA countries are planned to engage in this study.

The study will be conducted in paediatric hospitals or paediatric departments of *European Economic Area* member states where VTE patients of the evaluated age group are treated, depending on country regulations and requirements.

In order to assure assessment of representativeness of the PASS, all patients under 2 years who required anticoagulation and sign informed consent will be screened for potential participation in the study. Screening details will be entered in the Screening Log, which will contain final conclusion on study eligibility with clarification of screening failure if not enrolled in the PASS. If a patient completes all study entry criteria, a baseline part of the Screening / Baseline visit will be conducted, and the patient will enter an observational study period.

During the observational period safety outcomes, which comprise all specific clinical safety data connected with anticoagulation management of the children under 2 years of age, will be collected.

The study observational period is defined as a time period from the index date (i.e., initiation of DE administration) onwards up until DE administration discontinuation + 3 days of Residual Effect Period (REP) or switch to other anticoagulation therapy + 3 days of REP or planned end of 6 month observation time, whatever occurs earlier. Overall duration of the study observational period for any

patient will not exceed 6-month period of anticoagulation. Patients will not be followed outside the observational period.

Duration of the observational period will be as follows:

- up to 3 months from the day of DE initiation defined as index date for the treatment of acute VTE and
- up to 6 months from index date for prevention of recurrent VTE.

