Patients after completion of acute VTE treatment may continue anticoagulation due to unresolved VTE risk factors. The duration of the VTE treatment and secondary VTE prevention periods will be based on investigator judgement. Total duration of the observational period for this group will be performed until DE administration discontinuation + 3 days of REP or planned end of 6-month observation time, whatever occurs earlier.

Patient who completed acute VTE treatment and continued DE anticoagulation due to unresolved VTE risk factors will be considered as one unique patient. However, safety outcomes of each anticoagulation period will be evaluated within the corresponding cohort.

Anticoagulation of more than 6-month duration, if required due to the presence of unresolved VTE risk factors, will not be covered in this study setting.

The duration of anticoagulation outlined in this PASS study is in accordance with international guidelines for management of VTE paediatric patients [P19-00949], results and experience of the previous DE registrational studies, and reflect routine VTE paediatric care. The recommended duration of anticoagulation treatment is up to 3 months for children above one year of age. For neonates and infants (children under 1 year), the usual recommended treatment duration is 6 weeks. However, it may be extended, if the VTE clinical risk factors are unresolved at the end of the 6-week treatment period. Recommendations on the duration of anticoagulation for prevention of VTE recurrence depend on the presence of unresolved VTE clinical risk factors and may continue for an indefinite period of time. Final decision on the duration of VTE treatment and /or secondary prevention periods will be based on investigator's judgment.

Safety data collection will be conducted at Screening/Baseline and Follow up visits for both VTE treatment and prevention of recurrent VTE groups. Visit details provided in the Section 8.2.3. "Study visits".

The study is observational and does not entail any change in prescribing pattern or management policies which are left to the discretion of the treating physician. No special evaluation procedure is required.

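### The primary bleeding proportion mixes bleeding rate with length of the dabigatran course, and the protocol plans no exposure-adjusted estimate to set beside it

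*Protocol*

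**What the plan says.** The primary objective (section 7) is to estimate the incidence of any bleeding, major or non-major, in children under 2 years on DE. Section 8.7.1 gives the method: "Safety outcomes will be summarized as incidence with 95% CIs (using Wilson method"). The analysis is based "on all patients, who were treated with dabigatran at least once", and "no hypotheses will be tested".

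Section 8.1 defines observation as running from the index date "onwards up until DE administration discontinuation + 3 days of Residual Effect Period (REP"), or to a switch of anticoagulant, or to the planned end, whichever comes first. No minimum is set, and "Patients will not be followed outside the observational period". The ceiling is 3 months for acute treatment and 6 months for prevention. On course length, section 8.1 says: "The duration of the VTE treatment and secondary VTE prevention periods will be based on investigator judgement". It also links length to age: "For neonates and infants (children under 1 year), the usual recommended treatment duration is 6 weeks", against up to 3 months above one year. Section 8.2.3 places the follow-up visit at about 6 weeks or 3 months (acute) and about 3 or 6 months (prevention), again by investigator judgment. Section 8.2.1 expects duration to vary between sites.

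Sections 8.1 and 8.2.2 assign the safety outcomes of each anticoagulation period to its own cohort. Section 8.3.3 lists duration of DE among the data collected. Section 8.7 gives the intended use: "Safety outcomes from this single-arm study will be interpreted in the context of findings from the paediatric clinical developmental program", meaning DIVERSITY and the secondary prevention study.

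**The concern.** Wilson is an interval for a proportion x/n. A child who stops DE after two weeks without bleeding adds the same 0/1 to that figure as a child observed for six months without bleeding. The result therefore rises with longer courses and falls with shorter ones, even if the rate of bleeding per unit of time on drug is unchanged. The protocol states no person-time rate and no risk at a fixed time.

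Two features of the design make this matter. Course length is tied to age, so infants, who usually have the shorter courses, would tend to show a lower proportion for that reason alone. And the result is to be read beside two earlier studies, where a difference in observation length could pass for a difference in bleeding, or could hide one.

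**Working it through.** There is no planned rate or precision to reproduce. Section 8.5 sets 50 evaluable patients from anticipated usage and feasibility.

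**Inputs from the protocol:** course lengths of 6 weeks or 3 months (acute) and 3 or 6 months (prevention), from section 8.2.3. **Assumptions, because the protocol gives no figure:** the bleeding hazard, and 80/20 and 20/80 mixes of short and long courses in each cohort. The 3-day residual period is ignored here.

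**Step 1, risk by course length.** Take a constant hazard with 20% bleeding at 3 months (91.3 days): h = −ln(0.8)/91.3 per day, and risk at day d = 1 − exp(−h·d).

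- 6 weeks (42 days): 1 − 0.8^(42/91.3) = 9.8%
- 3 months: 20.0%
- 6 months (182.6 days): 1 − 0.8² = 36.0%

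**Step 2, expected proportion within each cohort.**

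- Acute, 80% short: 0.8 × 9.8 + 0.2 × 20.0 = 11.8%. Reversed: 0.2 × 9.8 + 0.8 × 20.0 = 18.0%.
- Prevention, 80% short: 0.8 × 20.0 + 0.2 × 36.0 = 23.2%. Reversed: 0.2 × 20.0 + 0.8 × 36.0 = 32.8%.

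**Step 3, sensitivity.** The front-loaded rows use a Weibull hazard of shape 0.5, with risk = 1 − exp(−H·(d/91.3)^0.5) and H = −ln(1 − risk at 3 months).

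| Assumed risk at 3 months | Hazard | 6 weeks / 3 months / 6 months | Acute, 80/20 → 20/80 | Prevention, 80/20 → 20/80 |
|---|---|---|---|---|
| 20% | constant | 9.8 / 20.0 / 36.0% | 11.8 → 18.0% | 23.2 → 32.8% |
| 20% | front-loaded | 14.0 / 20.0 / 27.1% | 15.2 → 18.8% | 21.4 → 25.7% |
| 10% | constant | 4.7 / 10.0 / 19.0% | 5.8 → 8.9% | 11.8 → 17.2% |
| 10% | front-loaded | 6.9 / 10.0 / 13.8% | 7.5 → 9.4% | 10.8 → 13.1% |

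The shift keeps its direction throughout and shrinks when bleeding is concentrated early.

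**Step 4, what a person-time rate adds.** Suppose 10 of 50 children bleed. Wilson gives 20% (11.2% to 33.0%) whatever the exposure. Now assume total time at risk of either 8.7 or 21.2 patient-years, which averages 8.7 × 12/50 = 2.1 or 21.2 × 12/50 = 5.1 months per child. Counting one first bleed per child, the rates with exact Poisson 95% intervals are:

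- 10/8.7 = 1.15 per patient-year (0.55 to 2.11)
- 10/21.2 = 0.47 per patient-year (0.23 to 0.87)

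One proportion is thus compatible with rates that differ by a factor of 21.2/8.7 = 2.4.

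**The case against.** The strongest reply is that the planned quantity is legitimate. Each child either bled during the course or did not. Wilson covers that proportion even when course lengths differ, and risk over a DE course as given in routine practice suits a routine-care safety study. This stands: a reader might infer that the interval is invalid, and it is not.

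The cohort split is a real mitigation. Among planned courses the spread within a cohort is about two-fold, apart from early stopping. A calculation that pools 6-week and 6-month courses across the two indications would show a larger swing, but it ignores the split. The split still leaves 6 weeks against 3 months, and 3 against 6 months, inside the cohorts. A child who moves from acute treatment to prevention also brings a shortened prevention period, because the total is capped at 6 months.

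The study is small and descriptive, and no formal comparison is planned. Sampling error is large: the Wilson interval for 10/50 runs from 11% to 33%. That is true, but the interval displays sampling error and does not display the effect of course length.

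The analysis plan is not shown and may add exposure-adjusted rates; nothing in the protocol forbids them. The point is therefore not that detail is missing. The protocol already names its main summary, and that summary needs a companion to serve the reading intended in section 8.7.

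**Conclusion.** The point holds in a limited form. The planned proportion is valid for what it measures, but it combines bleeding rate with course length and cannot be compared with the earlier studies without matching or adjusting for exposure. Under a constant hazard with 20% bleeding at 3 months, reversing an 80/20 mix moves it by about 6 percentage points in the acute cohort and about 10 in the prevention cohort. With a front-loaded hazard the shifts are about 4 in each. These sizes rest on assumed rates, hazard shapes and mixes.

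Two stronger readings are not supported. One is that the results cannot be set beside the earlier studies at all. The protocol does not report those studies' bleeding rates or observation lengths in under-2s, says that its own durations follow experience from the earlier registrational studies, and intends only a contextual reading. The other is that the figure reflects follow-up and not the drug's bleeding risk. By the formula above it reflects both.

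**What to change.** In section 8.7.1:

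1. Add first bleeding events per patient-time at risk with exact Poisson 95% intervals, by cohort and overall, for any bleeding and for major bleeding. Time at risk runs from the index date to the first bleed or the end of the observational period. For children who pass from acute treatment to prevention, state how time and events are divided between the cohorts.
2. Show the distribution of observation time, by cohort and overall.
3. Keep the Wilson proportion, labelled as risk over the DE course as given.
4. Optionally, add cumulative incidence of any bleeding at one fixed time per cohort, for example 6 weeks or 3 months for acute treatment and 3 months for prevention. State that stopping DE may be informative, since a bleed may itself end treatment. Several time points and outcomes would be too sparse with about 50 children.
5. In section 8.7, say that results will be read against earlier studies on the exposure-adjusted or same-time-point scale.

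The end of time at risk must match the window for counting events. Section 8.1 adds 3 days after a switch of anticoagulant, whereas the treatment-emergent definition in section 8.7.1 does not, so the two should be reconciled.

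The cost is some wording and a few more tables, with duration of DE already to be collected. Intervals will be wide, and a single person-time rate assumes a constant rate, which early bleeding would breach.
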